### **5.1.1.2 Enrollment Visit Inclusion Criteria:**

In addition to confirming all relevant Screening Visit Inclusion Criteria, women must meet all of the following criteria to be eligible for enrollment in the study.

1. Willing and able to provide Enrollment written informed consent;
2. After completion of metronidazole induction therapy or another CDC-recommended BV treatment, no clinical evidence of BV\* and absence of symptoms of BV\*\* at V1;  
\*As defined by  $\leq$  2 of 4 Amsel criteria.  
\*\*Defined as absence of vaginal discharge and odor consistent with BV.
3. Must have a negative urine pregnancy test at V1, if of childbearing potential;
4. Willing to refrain from any intravaginal products/medications\* other than the IP throughout the course of the trial;  
\* For example: douches, antifungal or antibacterial preparations, lubricants, contraceptive creams, gels, foams, sponges, spermicides.
5. Must agree to abstain from receptive oral, anal, and vaginal sexual intercourse one hour prior to IP administration and for 24 hours after;
6. Willing to refrain from using tampons or menstrual cups for 24 hours after IP administration.
7. Must be of non-childbearing potential\* OR must be using an effective method of birth control\*\* and must be willing to continue the method through the end of IP administration.

\*Defined as post-menopausal, or status post bilateral tubal ligation, or status post bilateral oophorectomy or status post hysterectomy.

\*\*Acceptable methods are defined as:

- a. IUDs or hormonal contraceptives for at least 30 days prior to using IP. Note: Intravaginal contraceptive rings (e.g., NuvaRing) are not acceptable forms of birth control for this study.
- b. Consistent use of a barrier method, including diaphragms or condoms, for at least 21 days prior to using IP.
- c. Abstinence from vaginal sexual intercourse for at least 21 days prior to using IP.
- d. Exclusively same-sex relationship.
- e. Monogamous relationship with vasectomized partner.

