### 6.1 Visit 0 (Day -15 to -8) Screening

- Potential participants will be provided with a description of the study (purpose and study procedures) and asked to read and sign the Screening Informed Consent form, (SIC). The SIC will be signed prior to performing any study procedures, including any screening procedures.
- Demographic information will be collected from the participant.
- Eligibility criteria will be reviewed with the participant.

At this juncture, if a potential participant is not eligible, information regarding reason for screen failure will be noted and the participant will not have any additional screening procedures completed.

- Complete medical history will be obtained by both interview of participants and review of medical records, if available, to assure eligibility.
- Vaginal symptoms such as odor, itching, irritation, and discharge will be reviewed with the participant.
- Sexual history for the past 30 days will be collected.
- A urine pregnancy test will be performed on all participants of childbearing potential and must be negative prior to administration of oral metronidazole or other CDC-recommend BV treatment induction therapy.
- All concomitant medications taken in the last 30 days will be recorded on the appropriate data collection form (DCF).
- A pelvic examination to include examination of external genitalia will be conducted using a non-lubricated speculum and swabs and samples obtained for analysis of Amsel criteria; KOH and saline microscopy for identification of yeast forms, trichomonas, and clue cells; NAAT for *C. trachomatis*, *N. gonorrhoeae*, and *T. vaginalis*; BD Max baseline test; future analysis, for participants who consented to future use of their specimens; and Gram staining

for Nugent scoring. Instructions for obtaining vaginal swab specimens for these assessments are outlined in the protocol-specific MOP. Gram stain Nugent scoring will be conducted in the Central Laboratory; all other testing will be conducted locally. A Pap smear should also be done for any participant who meets the following criteria and cannot provide documentation (which can include self-report) of a normal or ASCUS HPV negative Pap test within the prior 3 years: is 21 years of age or older and (a) has not had a hysterectomy or (b) has had a hysterectomy and has a history of CIN2+ in the past 20 years. If a Pap smear is conducted at V0, the results are not required prior to enrollment.

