- Participants with clinical evidence of VVC based on vulvovaginal signs (edema, erythema, and/or excoriation) and symptoms (vulvovaginal itching, burning, and/or irritation) will have a confirmatory vaginal *Candida* culture and treated as appropriate with oral fluconazole. Participants who cannot take oral fluconazole will be terminated from the study.
- Blinded IP based on randomization assignment will be provided to the participant in a prepared kit with other study supplies.

---

- Study protocol requirements and dosing instructions will be reviewed with the participant and a participant memory aid and written study instructions provided. Participants will be counseled to refrain from receptive oral, anal, and vaginal sexual intercourse 24 hours prior to the next study visit, as this can affect the accuracy of vaginal pH measurement.
- Participants will be scheduled to return for follow-up at Visit 2 (Day 29).
- Study staff will contact participants as a reminder for Visit 2 and to discuss adherence to IP and any barriers to IP use.

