## **7.2      Laboratory Evaluations**

### **7.2.1      Clinical Laboratory Evaluations**

At the screening visit, V0, diagnostic laboratory tests for determination of *C. trachomatis*, *N. gonorrhoeae*, and *T. vaginalis* (NAATs) will be performed locally. Vaginal Gram stain Nugent scoring for microbiologic confirmation of clinical findings will be conducted in the Central Laboratory. BD Max baseline testing will be conducted at a certified laboratory. Instructions for obtaining vaginal swab specimens for these assessments are outlined in the protocol-specific MOP.

A urine pregnancy test will be performed at all visits on all participants of childbearing potential. Screening and enrollment visit results must be negative and known prior to randomization on V1.

---

At all scheduled study visits a BD Max test will be conducted at a certified laboratory. At the enrollment and follow-up visits, vaginal Gram stain Nugent scoring for microbiologic confirmation of clinical findings will be conducted in the Central Laboratory. At the follow-up visits participants with clinically diagnosed VVC will have a confirmatory culture for vaginal *Candida* with speciation performed locally.

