6.3. Analysis Populations

Safety Population: This analysis population includes all randomized participants who received at least one dose of study treatment. Participants with any evidence of dosing according to the memory aid or study IP packaging return will be included in the Safety population.

Modified Intent-to-Treat (mITT) Population: This analysis population includes all randomized participants who are evaluable (see below). If a participant was enrolled more than once, (participants are allowed to be re-enrolled under PI's discretion for scenarios such as, the first enrollment terminated due to the COVID-19 shelter in place order or became ineligible after enrollment.) only the set of data from the most recent enrollment will be included in the mITT population.

The mITT population will be used as the primary efficacy analysis population.

Per-Protocol (PP) Population: This analysis population includes all randomized participants who are evaluable, complied with the assigned IP (see section 4.4.8), and returned to the study site for the TOC visit within the specified window (Visit 4 [Window: Day 85-91]) or were followed up to their diagnosis of recurrent BV. Participants who violated any inclusion/exclusion criterion at any point during the study or engaged in receptive oral, anal, or vaginal sexual intercourse within 24 hours prior to a study visit will be excluded from the PP population. If a participant was enrolled more than once, (participants are allowed to be re-enrolled under PI's discretion for scenarios such as, the first enrollment terminated due to the COVID-19

shelter in place order or became ineligible after enrollment.) only the set of data from the most recent enrollment will be included in the PP population.

In the unlikely event of an error in randomization or IP administration (i.e., incorrect treatment), participants will be grouped by the treatment they actually received in safety analyses but will be grouped by their intended randomized assignment in efficacy analyses.

Evaluable is defined as follows:

- Negative STI tests taken at baseline (*C. trachomatis*, *N. gonorrhoeae*, or *T. vaginalis*);
- For participants 21 years of age or older, documentation of or self-report of a normal or ASCUS HPV negative Pap test prior to screening, or a Pap smear performed at screening/enrollment with normal result

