Treatment Group	Subject ID	MH Number	Medical History Term	Condition Start Day	Condition End Day	MedDRA System Organ Class	MedDRA Preferred Term
TOL-463 Vaginal Insert/Placebo	xxxxxx	xx	xxxxxx	ddMMMyyyy	ddMMMyyyy	xxxxxx	xxxxxx
TOL-463 Vaginal Insert/Placebo	xxxxxx	xx	xxxxxx	ddMMMyyyy	ddMMMyyyy	xxxxxx	xxxxxx

Note: This listing includes subjects who had pre-existing and/or concurrent medical conditions among all enrolled subjects.

Listing 12: Concomitant Medications

Treatment Group	Subject ID	CM Number	Medication	Medication Start Day	Medication End Day	Indication	Taken for an AE? (AE Description; Number)	Taken for a condition on Medical History? (MH Description; Number)	ATC Level 1 (ATC Level 2)
TOL-463 Vaginal Insert/Placebo	xxxxxx	xx	xxxxxx	ddMMMyyyy	ddMMMyyyy	xxxxxx	Yes/No xxxxx; xx	Yes/No xxxxx; xx	xxxxxx (xxxxxx)
TOL-463 Vaginal Insert/Placebo	xxxxxx	xx	xxxxxx	ddMMMyyyy	ddMMMyyyy	xxxxxx	Yes/No xxxxx; xx	Yes/No xxxxx; xx	xxxxxx
TOL-463 Vaginal Insert/Placebo	xxxxxx	xx	xxxxxx	ddMMMyyyy	ddMMMyyyy	xxxxxx	Yes/No xxxxx; xx	Yes/No xxxxx; xx	(xxxxxx)

Listing 13: Screening and Baseline Gynecologic and Sexual History - All Enrolled Subjects

Treatment Group	Subject ID	Screening			Baseline				
		Treated for BV in the Past 30 Days	Currently Use Sanitary Product	No. of times has the subject had BV in the past 12 months	First Day of Last Menstrual Period ^a	Douched or Applied Any Intravaginal Products or Medications	Had Sex Since Screening Visit	Type of Sex	How often did the subject use a condom for Vaginal Sex?
TOL-463 Vaginal Insert /Placebo	xxxxxx	Yes/No [Oral Metronidazole, Vaginal Metroge, Vaginal Clindamycin, Other:Specify]	Yes/N/A [Pads/pantyliners, Menstrual Cups, Tampons, Other: Specify]	x	DDMMYY/N/A	Yes/No	Yes/No	Vaginal sex, Receptive oral sex, Anal/rectal sex/ N/A	Never/Less than 50% of the time/About 50% of the time/ More than 50% of the time/Always/ N/A
TOL-463 Vaginal Insert /Placebo	xxxxxx	Yes/No [Oral Metronidazole, Vaginal Metroge, Vaginal Clindamycin, Other:Specify]	Yes/N/A [Pads/pantyliners, Menstrual Cups, Tampons, Other: Specify]	x	DDMMYY/N/A	Yes/No	Yes/No	Vaginal sex, Receptive oral sex, Anal/rectal sex/ N/A	Never/Less than 50% of the time/About 50% of the time/ More than 50% of the time/Always/ N/A

^a If the subject did not have period since screening, use the response collected at the screening visit; N/A if subject is post-menopausal or amenorrheic on current hormonal birth control method.

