Listing 14: Follow-up Gynecologic and Sexual History - All Enrolled Subjects

Treatment Group	Subject ID	Visit	Study Day	Douched or Applied Any Intravaginal Products or Medications Since Last Visit	Had Sex Since Last Visit	Type of Sex (Sex in the Past 24 Hours before Visit)	How often did the subject use a condom for Vaginal Sex?
TOL-463 Vaginal Insert /Placebo	xxxxxx	xx	xx	Yes/No	Yes/No	Vaginal sex (Yes/No), Receptive oral sex (Yes/No), Anal/rectal sex (Yes/No),/ N/A	Never/Less than 50% of the time/About 50% of the time/ More than 50% of the time/Always/ N/A
TOL-463 Vaginal Insert /Placebo	xxxxxx	xx	xx	Yes/No	Yes/No	Vaginal sex (Yes/No), Receptive oral sex (Yes/No), Anal/rectal sex (Yes/No),/ N/A	Never/Less than 50% of the time/About 50% of the time/ More than 50% of the time/Always/ N/A

Listing 15: Compliance Data

Implementation Notes:

Continue for all subjects.

If all subjects received the correct treatment, only display a single “Treatment Group” column.

Include data at unscheduled visits.

Study Days of Inserts Administration column: concatenate study days by a comma.

Sort by planned treatment group, USUBJID where all subjects who completed the study listed before all subject who terminated the study, Visit number.

Planned Treatment Group	Actual Treatment Group	Subject ID	Study Day of Completion /Early Termination	Visit	Number of Inserts Used/Unused	Study Days of Insert Administration	Compliant Since Last Visit ^a (Assessment Day)	Compliance Determination Throughout the Study ^b
TOL-463 Vaginal Insert/Placebo	TOL-463 Vaginal Insert/Placebo	xxxxxx	x / N/A or N/A / x	02	x/x	x, x, x, x, x, x, x, x	Yes/No (x)	Yes/No
				03	x/x	x, U, x, x, x, x, x, x	Yes/No (x)	
				04	x/x	x, x, x, x, x, x	Yes/No (x)	

Notes: For early terminated participants, compliance with study treatment will be determined through study participation.

When a study day of insert administration is unknown, it is denoted by “U”.

^a The participant did not miss ≥ 2 consecutive or ≥ 3 nonconsecutive doses of IP since the last assessment, as recorded in data collection form.

^b For cases that could not be programmatically determined, the determination of treatment compliance throughout the study was provided by a blinded case review committee.

Listing 16: Pregnancy Reports**Pregnancy Reports – Maternal Information**

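### The SAP's 24-hour sexual-activity exclusion tests suppressed women at three follow-up visits but a Visit 2 recurrer at only one, so per-protocol membership depends on the outcome

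*SAP*

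**What the plan says.** SAP 6.3 defines the PP set as evaluable, compliant women who either attended V4 in window or were followed to a diagnosis of recurrent BV. It then adds that a woman who "engaged in receptive oral, anal, or vaginal sexual intercourse within 24 hours prior to a study visit will be excluded from the PP population". It does not say which visits count, or whether unscheduled visits do.

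The reason for the rule is in Protocol 6.2. Women are told at V1 to abstain "24 hours prior to the next study visit, as this can affect the accuracy of vaginal pH measurement". The same counselling is repeated at V2 for V3 and at V3 for V4 (Protocol 6.3.1 and 6.3.2). None is given at V0. In the SAP listing shells, a field for sex in the 24 hours before the visit appears only in the follow-up history (Listing 14). The screening and baseline history (Listing 13) asks "Had Sex Since Screening Visit" and has no 24-hour field.

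Protocol 5 ends a woman's participation once more than two Amsel criteria are found at a follow-up visit. The PP definition in Protocol 10.5.1 does not contain the 24-hour rule, and SAP Table 4 has no row for this exclusion. SAP 8.1 and 8.2 use the PP set to repeat the primary analysis and all secondary efficacy analyses.

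**The concern.** The rule is meant to remove women whose pH reading may be unreliable. As written, one lapse before any visit removes the woman altogether, and the number of chances to lapse depends on how long she stays free of BV. Suppressed women stay longest and are therefore the most likely to be deleted. This would raise PP recurrence in both arms and shrink the PP set. If the arms differ in when recurrences occur, it would also distort the comparison that is meant to corroborate the primary result.

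**Working it through.** **Inputs from the documents.** Recurrence is 40% on placebo and 20% on TOL-463, with 1:1 allocation and 200 evaluable women (SAP 5). The test is a two-sided 5% chi-square (Protocol 10.1). There are up to three scheduled follow-up visits, and recurrence ends participation (Protocol 5).

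**Assumptions.** p is the probability of sex in the 24 hours before a visit. It is taken as the same at every visit, independent between visits, and independent of arm and outcome. Recurrences are first spread evenly over V2, V3 and V4. Unscheduled visits are not modelled.

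**The plan's own figure.** With 100 per arm, power = Φ[(0.20·√100 − 1.96·√(2·0.3·0.7)) / √(0.24+0.16)] = Φ[(2 − 1.270)/0.632] = Φ(1.154) = 87.6%. This agrees with the stated minimum of 85%. The planning calculation is not in question.

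**Retention under the rule.**
- Suppressed woman, or V4 recurrer: (1−p)³
- V3 recurrer: (1−p)²
- V2 recurrer: 1−p

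At p=10% these are 72.9%, 81.0% and 90.0%. With even timing, recurrers as a group are kept at (0.900+0.810+0.729)/3 = 81.3%, against 72.9% of suppressed women.

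**PP recurrence** = r·R / [r·R + (1−r)·S], where r is true recurrence, R the retention of recurrers and S the retention of suppressed women. At p=10%:
- Placebo: 0.4×0.813 = 0.3252 and 0.6×0.729 = 0.4374, so 0.3252/0.7626 = 42.6%
- TOL-463: 0.2×0.813 = 0.1626 and 0.8×0.729 = 0.5832, so 0.1626/0.7458 = 21.8%

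| p | PP recurrence, placebo/TOL-463 | Difference (points) | Ratio | Kept, placebo/TOL-463 |
|---|---|---|---|---|
| 0 | 40.0% / 20.0% | 20.0 | 0.50 | 100% / 100% |
| 5% | 41.3% / 20.8% | 20.4 | 0.505 | 87.6% / 86.7% |
| 10% | 42.6% / 21.8% | 20.8 | 0.511 | 76.3% / 74.6% |
| 20% | 45.9% / 24.1% | 21.8 | 0.526 | 56.7% / 54.0% |

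Differences are taken before rounding. The average loss at p=10% is 1 − (0.7626+0.7458)/2 = 24.6%. Starting from 100 otherwise qualifying women per arm, power in the PP set is then 78.7%.

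**Sensitivity to timing.**
- All recurrences at V4: everyone is checked three times, and the proportions stay at 40%/20%.
- All recurrences at V2: 45.1%/23.6% at p=10% and 51.0%/28.1% at p=20%.
- No treatment effect (40% in both arms) and equal timing: both arms move to the same figure, with no between-arm bias.
- No treatment effect, one arm recurring only at V2 and the other only at V4, p=20%: 51.0% against 40.0%. This is an extreme case, shown only to establish that the bias can arise.

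**One check per woman.** Retention is 1−p for everyone, so PP recurrence stays at 40%/20% for any p. Power from 100 per arm is 85.9%, 83.9% and 79.4% at p=5%, 10% and 20%.

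**The case against.** The best defence is that suppression means two or fewer criteria at each observed follow-up visit (Protocol 10.5.4.1, SAP 4.5.1), so every reading of a suppressed woman contributes to her outcome and every reading deserves the check. The documents do not say in which direction sex shifts pH, so a misread V2 could hide a recurrence. That possibility stands, but it does not require deleting the woman. Suppression is judged on observed visits, and the PP definition demands only V4 in window or follow-up to diagnosis. A doubtful V2 or V3 reading in a woman who is negative at V4 can be handled as an unobserved one.

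Other points on this side also stand:
- With even timing and low p, the treatment contrast barely moves.
- Symptomatic women are asked to attend unscheduled visits, where recurrence can be diagnosed. If those visits count, recurrers gain exposure to the rule and the asymmetry narrows.
- The compliance rule and the V4 window also bear more heavily on women who stay in longer.
- The mITT set carries the primary analysis.

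A reader might go further and infer that women will be dropped for sex before V0 or V1, before any instruction was given. The wording allows this: in "At all scheduled study visits a BD Max test will be conducted at a certified laboratory" the term includes V0 and V1, since the schedule of events marks that test at both. But the counselling and the 24-hour field line up at V2 to V4, and the baseline listing gives nothing on which to apply the rule earlier. On the documents available, which exclude the case report forms and the manual of procedures, this is a gap in wording.

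A reader might also infer that V1 eligibility is biased by an unprotected pH reading. The documents do not show that. pH is one of four criteria, absence of symptoms is also required, no direction of error is given, and the assessment precedes randomization.

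**Conclusion.** The concern holds in a limited form. The SAP 6.3 rule makes PP exclusion depend on the outcome, raises PP recurrence in both arms and costs a substantial share of the set. At an assumed p of 10% with even timing, recurrence rises by 2.6 and 1.8 points, the difference by 0.8 points, and about 25% of otherwise qualifying women are lost. The size rests on p, which the documents do not give, on its independence from arm and outcome, on the timing of recurrences, and on leaving out unscheduled visits.

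The figures do not support reading this as a serious bias in the treatment effect. That would need recurrence timing to differ between arms, which is possible but not established. The primary mITT analysis and the sample size are unaffected.

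**What to change.** Change SAP 6.3 only, before treatment codes are opened:
- Apply the 24-hour rule once per woman: at the scheduled or unscheduled visit where recurrence was diagnosed, or at V4 if she did not recur.
- State that V0 and V1 are not covered.
- Add this reason to the PP exclusions in Table 4.

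Under the assumptions above, retention is then 1−p regardless of outcome. Because sexual history at unscheduled visits is collected at the site investigator's discretion (Protocol 6.4), the text should also say how a missing 24-hour answer is treated there.

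The cost is a sentence or two and one table row. Women with a lapse before a non-decisive visit stay in the PP set, and the compliance and V4-window criteria still fall more heavily on suppressed women. New counselling at V0 or a new 24-hour question at V1 is not proposed: SAP 5 records that the study closed early, so neither could help now.

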## **5.2 Withdrawal from the Study, Discontinuation of Study Product, or Study Termination**

### **5.2.1 Withdrawal from the Study or Discontinuation of the Study Product**

#### **5.2.1.1 Reasons for Study Withdrawal**

Participants may voluntarily withdraw their consent for further study participation at any time and for any reason without penalty or prejudice to future medical care.

Participants may be required to withdraw from further study participation after discussion with the investigator for the following reasons:

- AE(s) judged to be severe (Grade 3) and related to IP
- SAE(s) judged to be related to IP
- Diagnosis of VVC at any follow-up visits, V2 or V3, or unscheduled visit(s) and cannot be treated with oral fluconazole
- A Pap test result from V0 that was anything other than normal or ASCUS HPV negative; participant is no longer eligible for the study.
- Medical disease or condition, or new clinical finding(s) for which continued participation, in the opinion of the investigator might compromise the safety of the participant, interfere with the participant's successfully completion of the study, or interfere with the evaluation of responses
- Violation of eligibility criteria
- Significant deviation from the treatment plan specified in the protocol (i.e., incorrect administration of IP, failure to attend study visits)
- Participant lost to follow-up
- At the discretion of the investigator

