### **7.1.1 Assessment of Concomitant Medications/Treatments other than Study Product**

Administration of any medications, therapies, or vaccines will be recorded on the appropriate DCF. Concomitant medications will include all medications taken 30 days prior to the initial screening visit V0, through V4 or early termination, whichever occurs first. Prescription and over-the-counter drugs will be included, as well as herbs, vitamins, and supplements.

Participants who have received study IP and are subsequently diagnosed with a concomitant infection that requires systemic antibiotics will receive treatment according to the local clinic's standard protocols but will be considered non-evaluable for efficacy and terminated from the study. However, participants who have received study IP and are subsequently diagnosed with VVC can remain in the study and be considered evaluable for efficacy if they are appropriate candidates for oral fluconazole therapy.

---

At the discretion of the site PI, use of new medication should prompt evaluation for the presence of a new diagnosis of chronic medical disease or condition.

Medications that might interfere with the evaluation of the IP should not be used unless absolutely necessary.

Refer to [Section 5](#) (Selection of Participants and Study Enrollment and Withdrawal) for medications that are prohibited for study eligibility and throughout study participation.

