### 10.5.1 Analysis Populations

Safety Population: This analysis population includes all randomized participants who received at least one dose of study treatment.

Modified Intent-to-Treat (mITT) Population: This analysis population includes all randomized participants who are evaluable.

The mITT population will be used as the primary efficacy analysis population.

Per-Protocol (PP) Population: This analysis population includes all randomized participants who met all inclusion/exclusion criteria throughout the study, are evaluable (defined below), complied with the assigned IP, and returned to the study site for the TOC visit within the specified window (Visit 4 [Window: Day 85-91]) or were followed up to their diagnosis of recurrent BV.

Evaluable is defined as follows:

- Negative STI tests taken at baseline (*C. trachomatis*, *N. gonorrhoeae*, or *T. vaginalis*);
- For participants 21 years of age or older, documentation of or self-report of a normal or ASCUS HPV negative Pap test prior to screening, or a Pap smear performed at screening/enrollment with normal result

A participant is compliant with the study treatment if she misses  $\leq 2$  non-consecutive doses of IP per month, as assessed by participant memory aid and returned IP and packaging at each follow up visit (V2, V3, V4).

In the unlikely event of an error in randomization or IP administration (i.e., incorrect treatment), participants will be grouped by the treatment they actually received in safety analyses but will be grouped by their intended randomized assignment in efficacy analyses.

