9.9. Other Laboratory Measures

[Listing 21](#) will present the results of NAAT STI tests (C. trachomatis, N. gonorrhoeae, or T. vaginalis) Pap smear records and test and screening/enrollment for evaluable definition (see section [6.3](#)).

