Early Discontinuation from Treatment ^d	x	xx	x	xx	x	xx
Early Termination from Study ^b	x	xx	x	xx	x	xx

^a Received Treatment includes subjects who successfully received at least one dose of study treatment. It is unknown whether subjects received at least one dose if they were terminated early before Visit 2 and a Study Product Dispensing assessment at the early termination visit could not be conducted.

^b Completed Follow-up includes subjects who remained BV suppressed and were followed-up through Visit 4 as well as subjects whose participation ended prior to Visit 4 due to a clinical BV diagnosis. Terminated Early includes subjects who terminated from the study early for reasons other than a clinical BV diagnosis.

^c A blinded case review committee reviewed subjects' data to determine treatment compliance throughout the study for each subject.

^d Subjects who discontinued treatment due to RBV are included.

Table 4: Analysis Populations by Treatment Group

Analysis Populations	Reason Subjects Excluded	TOL-463 Vaginal Insert (N=X)		Placebo (N=X)		All Subjects (N=X)	
		n	%	n	%	%	n
Eligible for Safety Analysis Population	N/A	x	xx	x	xx	x	xx
Excluded from Safety Analysis Population	Any Reason	x	xx	x	xx	x	xx
	Did not receive at least one dose of study product	x	xx	x	xx	x	xx
Eligible for Modified Intent-to-Treat Analysis (mITT) Population	N/A	x	xx	x	xx	x	xx
Excluded from for Modified Intent-to-Treat Analysis (mITT) Population	Any Reason	x	xx	x	xx	x	xx
	Positive NAAT test results at baseline for C. trachomatis, N. gonorrhoeae, or T. vaginalis	x	xx	x	xx	x	xx
	HPV Criterion ^a	x	xx	x	xx	x	xx
Eligible for Per-Protocol (PP) Analysis Population	N/A	x	xx	x	xx	x	xx
Excluded from Per-Protocol (PP) Analysis Population	Any Reason	x	xx	x	xx	x	xx
	Did not meet inclusion/exclusion criteria	x	xx	x	xx	x	xx
	Positive NAAT test results at baseline for C. trachomatis, N. gonorrhoeae, or T. vaginalis	x	xx	x	xx	x	xx
	HPV Criterion ^a	x	xx	x	xx	x	xx
	Was not compliant with study product	x	xx	x	xx	x	xx
	Did not return to study site for the TOC visit within the specified window (Visit 4, Day 85-91)	x	xx	x	xx	x	xx
	Was not followed up to the diagnosis of recurrent BV	x	xx	x	xx	x	xx

Notes: N=Number of all enrolled subjects

^a For participants 21 years of age or older, documentation of or self-report of abnormal, or ASCUS HPV Positive Pap test prior to screening, or Pap smear performed at screening/enrollment with abnormal result.

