Treatment Group	Subject ID	Normal or ASCUS HPV Negative Pap Test Within the Past 3 Years ^a	Pap Smear Performed (Study Day)	NAAT testing for chlamydia (Study Day)	NAAT testing for gonorrhea (Study Day)	NAAT testing for trichomoniasis (Study Day)
TOL-463 Vaginal Insert/Placebo	xxxxxxx	Yes/No/N/A	Normal / ASCUS HPV Negative/ Abnormal: specify (-x)	Negative/Positive/Indeterminate (-x)	Negative/Positive/Indeterminate (-x)	Negative/Positive/Indeterminate (-x)

^a N/A if the subject is <21 years of age or has had a hysterectomy without history of cervical intraepithelial neoplasia grade 2+ (CIN2+) in the past 20 years.

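### The evaluable rule that defines the primary mITT mishandles the screening Pap: it omits ASCUS HPV negative, has no branch for women who need no Pap, and is not mirrored by SAP Table 4 footnote a

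*SAP*

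**What the plan says.** Protocol 10.5.1 defines the mITT, the primary efficacy population, in one line: "This analysis population includes all randomized participants who are evaluable". SAP 6.3 uses the same definition. Evaluable has two parts in both documents: negative baseline STI tests and, from age 21, a Pap condition. The Pap condition is met by a documented or self-reported normal or ASCUS HPV-negative Pap before screening, with no time limit, "or a Pap smear performed at screening/enrollment with normal result".

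Four other places bear on the same women:

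- Protocol 5.2.1.1 lists as a withdrawal reason "A Pap test result from V0 that was anything other than normal or ASCUS HPV negative; participant is no longer eligible". An ASCUS HPV-negative V0 Pap is therefore acceptable. Inclusion criterion 5 says that V0 Pap results need not be available before enrollment.
- The note to inclusion criterion 5 limits the mandatory V0 Pap to women without a hysterectomy, or with one and a CIN2+ history in the past 20 years. Listing 21 gives N/A to a woman who is under 21 "or has had a hysterectomy without history of cervical intraepithelial neoplasia grade 2+ (CIN2+) in the past 20 years".
- SAP 9.9 says that Listing 21 presents "Pap smear records and test and screening/enrollment for evaluable definition". That listing prints the V0 result as "Normal / ASCUS HPV Negative/ Abnormal: specify" and records an earlier qualifying Pap only within the past 3 years.
- SAP Table 4, footnote a, describes the Pap exclusion from the mITT as an abnormal "or ASCUS HPV Positive Pap test prior to screening, or Pap smear performed at screening/enrollment with abnormal result".

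On antibiotics, Protocol 7.1.1 says that women who need systemic antibiotics after receiving study product "will be considered non-evaluable for efficacy and terminated from the study". SAP 4.4.7 excludes them from per-protocol analyses only.

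**The concern.** One rule should decide who enters the primary population, and it should agree with the eligibility rules and with the table that reports exclusions. Here an eligible randomised woman can be removed because of a Pap result that the protocol accepts elsewhere, or because she lacks a Pap that she was never asked to have. Neither reason has anything to do with BV. Two programmers, one working from SAP 6.3 and the other from Table 4 footnote a, could build different primary populations from the same data. V0 Pap results may also arrive after randomisation, so a choice of reading made late would be made among women already assigned to treatment. It needs to be fixed before unblinding.

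**Working it through.** **Design figures first.** Inputs from Protocol 10.2 and 10.1: 40% recurrence on placebo, 20% on TOL-463, 1:1 allocation, 200 evaluable, Pearson chi-square test at two-sided 5%, 80% of enrolled women evaluable.

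Power = Φ[(Δ − 1.96·SE0)/SE1], with SE0 = √(2·p̄(1−p̄)/n), SE1 = √((p1(1−p1)+p2(1−p2))/n), Δ = 0.20, p̄ = 0.30.

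- n = 100 per arm: SE0 = 0.0648, SE1 = 0.0632, power = Φ(1.154) = 0.876. Exact enumeration of the Pearson test gives 0.880. The stated minimum of 85% is met.
- Enrollment: 200/0.80 = 250, as stated.

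**Membership, case by case.** All cases are randomised women aged 21 or older with negative STI tests.

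| Case | Earlier Pap | V0 Pap | Protocol 10.5.1 / SAP 6.3 | Table 4 footnote a |
|---|---|---|---|---|
| 1 | none | ASCUS HPV negative | out | not excluded* |
| 2 | none | none, not required | out | not excluded |
| 3 | abnormal | normal | in | excluded |
| 4 | normal, over 3 years old | abnormal | in | excluded |
| 5 | normal, within 3 years | none, not required | in | not excluded |

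*Listing 21 prints ASCUS HPV negative as a level separate from abnormal. If the footnote's abnormal means anything other than normal, it excludes her too, and then the footnote also conflicts with Protocol 5.2.1.1.

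Only case 5 agrees on every reading. Cases 1 and 2 are the eligible women whom the rule drops. Case 3 shows why the footnote is not the complement. SAP 6.3 joins two ways of qualifying with *or*, so exclusion requires failing both. The footnote joins two ways of being excluded with *or*, so failing one is enough. The footnote also requires a positive abnormal finding, so a woman with no Pap at all never meets it, whether or not she needed one.

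**Look-back.** The 6.3 limb for an earlier Pap has no time limit, while inclusion criterion 5 and Listing 21 use 3 years. As printed, Listing 21 cannot show a qualifying Pap older than that, and it does not separate an abnormal earlier Pap from none. Case 4 arises from this mismatch: the old Pap triggers a V0 Pap under the eligibility rule but still qualifies her under 6.3.

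**Size.** The documents give no counts. If 1 to 6 of the planned 200 were lost (an assumed range):

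- 199/2 = 99.5 per arm: power 0.874.
- 194/2 = 97 per arm: power 0.866.

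**Antibiotics, side by side.** Protocol 7.1.1 says non-evaluable. Protocol 10.5.1 has no antibiotic item in its definition, SAP 6.3 has the same definition, and Table 4 lists no such mITT exclusion. SAP 4.4.7 removes these women from the PP population only. So they stay in the mITT, although no single sentence says so outright.

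**The case against.** The strongest reply is that very few women are involved. A V0 Pap is needed only where no qualifying Pap within 3 years can be shown. Case 4 is largely dealt with by Protocol 5.2.1.1, which calls that woman no longer eligible. A woman who needed a Pap and had none is an eligibility deviation, and the protocol grants no exemptions. The table above counts combinations, not women, and some women with a hysterectomy will qualify through an old normal Pap. All of this stands, and it limits the size of the problem. It does not make the rule right for cases 1 to 3. Nor does the stricter V0 limb look deliberate, since Protocol 5.2.1.1 applies the wider standard to the V0 Pap by name.

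On antibiotics, Protocol 5.2.1.2 sends readers to 10.5.1 for analysis populations, and the SAP follows 10.5.1. Membership is therefore settled, and 7.1.1 is the sentence out of line. That also stands.

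A reader might infer more than the documents support:

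- That every ASCUS HPV-negative V0 result removes a woman. It does so only if she has no earlier qualifying Pap.
- That the SAP departs from the protocol on the Pap. The limb is worded the same in both, so the defect is shared.
- That the antibiotic wording costs power or biases the primary comparison. Any such effect would come from SAP 6.5, which scores undetermined status as failure for every reason alike. Protocol 10.5.4.1 leaves imputation details to the SAP, and the documents give no antibiotic termination rates. Reconciling 7.1.1 changes nothing in how these women are analysed.

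**Conclusion.** The Pap part of the evaluable rule is wrong as written in both documents, and Table 4 footnote a does not report the exclusions that the rule produces. Eligible randomised women can leave the primary mITT for reasons that the protocol does not otherwise recognise. The number is unknown and probably small. On the assumed loss of 1 to 6 of 200, split evenly between arms, power falls by at most 0.01 (0.876 to 0.866). That figure applies to the planned size only, because SAP 5 records that the study closed early. The case for correction is consistency of the primary population, not power. The antibiotic point is a real conflict within the protocol, but one of wording only.

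**What to change.** Before unblinding:

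1. In SAP 6.3 and Protocol 10.5.1, widen the second Pap limb to: *a screening or enrollment Pap that is normal or ASCUS HPV negative, or no Pap required*. If the protocol is closed to amendment, declare the change in SAP 15.
2. Use the same look-back for the earlier Pap in SAP 6.3 and Listing 21. With 3 years, the listing already matches. With no limit, it needs a further column and the data to fill it.
3. Rewrite Table 4 footnote a as the exact complement: *aged 21 or older, Pap required, no qualifying earlier Pap, and screening or enrollment Pap missing or with any other result*. Cases 1 to 3 are then in by both texts, and case 4 follows from the look-back chosen. No separate precedence rule is needed.
4. Reconcile Protocol 7.1.1 with Protocol 10.5.1 and SAP 4.4.7/6.3 on the analysis status of antibiotic-terminated women, and note the difference from 7.1.1 in SAP 15, which at present declares none. The termination rule and SAP 6.5 are not touched. A supportive table in the Table 7 format, leaving out those whose status is undetermined, is optional; it would condition on a post-randomisation event.

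The cost is one clause in two places, one footnote, one protocol sentence and a sentence or two in SAP 15. No new data are needed if the look-back is 3 years.
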